16.2. Appendix 2 - Trial management / responsibilities

Responsibilities will be detailed in the co-sponsorship and participating site agreements.

16.2.1. Participant registration/randomisation procedure

TCTU TRuST web-based randomisation system will be used.

Sites will be provided with a randomisation guide detailing the web-based randomisation system process. Prior to recruitment, individuals delegated this task will be given an individual username and password upon completion of training.

16.2.2. Data management

Data management will be overseen by TCTU Data Management Team.

Local sites will be expected to enter data directly on to the eCRF. Worksheets will be provided to facilitate this process, but their use is not mandatory. Worksheets, where used, will not be used for monitoring purposes.

All data from participants should be entered on the eCRF within 7 days of the last data collection point for that participant.

Data queries will be generated by the Data Management Team and should be addressed within 2 weeks.

16.2.3. Preparation and submission of amendments

TCTU Trial Management Team will be responsible for working with the CI to submit any amendments.

16.2.4. Preparation and submission of Annual Safety Report/Annual

TCTU Trial Management Team will be responsible for liaising with the CI to submit REC annual reports. The Sponsor Pharmacovigilance Team will be responsible for liaising with the CI to submit DSURs.

16.2.5. Data protection/confidentiality

The CI and trial staff will comply with the requirements of the Data Protection Act 2018, GDPR and the Data Protection Act 2018, or any subsequent amendment or replacement thereof regarding the collection, storage, processing and disclosure of personal data. The CI and trial staff will also adhere to the NHS Scotland Code of Practice on Protecting Participant Confidentiality or local equivalent.

16.2.6. Trial documentation and archiving

Archiving trial site data will be the responsibility of individual sites. Payment for archiving will be provided as per site agreement.

16.3. Appendix 3 – Authorisation of participating sites

16.3.1. Required documentation

The following data should be made available to TCTU Trial Management Team prior to site initiation:

- PI CV, signed and dated within the last 2 years
- PI GCP certificate
- Protocol signature page, signed and dated by PI
- Copy of signed Participating Site Agreement
- Copy of NHS R&D confirmation of capacity and capability
- Copy of the Delegation Log.

The following data should be made available and held within the ISF/Pharmacy Site File prior to site initiation:

- CV, signed and dated for all trial staff listed on Delegation Log
- GCP certificate for all trial staff listed on Delegation Log

16.3.2. Procedure for initiating/opening a new site

Site Initiation will be performed by Monitors and TCTU Trial Management Team and may be on site and/or remote.

TCTU Trial Management Team will initiate release of trial drug to the site after NHS R&D confirmation of capacity and capability.

16.3.3. Principal Investigator responsibilities

The PI's legal responsibilities will be listed in the Participating Site Agreement. A summary is given below:

- Attendance at the site initiation meeting
- Training of new members of trial staff in the protocol and its procedures,
- Ensuring that the ISF is accurately maintained
- Dissemination of important safety or trial related information to all stakeholders within their site
- Safety reporting within the required timelines
- Ensuring data entry to eCRF and responses to data clarification queries are completed within the required timelines
- Certify data entered on eCRF is correct and complete
- Ensuring any trial staff coming into contact with participants have the appropriate Personal Protective Equipment and training in its use
- Archiving of site trial data

16.4. Appendix 4 – Schedule of Procedures

	Visit 1 Screening	Visit 2 Baseline	Visit 3	Visit 4	Visit 5	Visit 6	Safety visit
	Days -35 to 0	Day 0	Day 7	Day 14	Day 28	Day 56	If required
Informed consent	X						
Eligibility check	X	X					
Demographics	X						
Medical history	X						
Concomitant medications	X	X	X	X	X	X	X
Physical examination	X						
Height & weight	X						
Record AEs		X	X	X	X	X	X
Record exacerbations		X	X	X	X	X	X
BP, pulse, temp, O ₂ stats	X	X	X	X	X	X	X
EKG	X						
6 minute walk test		X			X		
Post bronchodilation spirometry	X	X	X	X	X	X	X
QoL-B	X	X	X	X	X	X	
BIM baseline		X					
BIM follow-up			X	X	X	X	
BEST diary		X	X	X	X		
Full blood count, urea and electrolytes, liver function tests	X			X	X	X	X
Research blood sample for endpoint analyses		X	X	X	X	X	
Sputum sample for screening eligibility (NEATstik) ^a	X						
Research sputum sample for endpoint analyses		X	X	X	X	X	
Nasal sample		X			X		
Pregnancy test, if required	X	X	X	X	X		
Randomisation		X					
Dispensing of trial drugs		X					
Drug accountability					X		
Sub-study only							
Pulse wave velocity (PWV)		X			X	X	
Full-field Laser perfusion imaging (FLPI)		X			X	X	
Waist & Hip measurement		X					

^a If NEATSTIK is not available for screening, a frozen sputum sample will be shipped to the central laboratory in Dundee where the immunoassay will be performed and used to confirm eligibility.

Missed trial assessments or trial medication, or visits completed outside the visit window, will not be reported as breaches, where this is due to participant choice or a clinical decision.

Visits should be every as per schedule wherever possible. If a participant is unable to attend on the day of visit a delay of up to 2 days is accepted.

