Participants will be randomized to one of the open treatment arms they have been deemed eligible for, or usual care. Treatment will be administered for 28 days, a period which should be sufficient to demonstrate robust anti-inflammatory effects based on previous studies ([name] et al. 2020). All compounds are not currently used in the treatment of bronchiectasis as long-term therapies but have in vitro or in vivo evidence that they target neutrophilic inflammation and are widely available generic drugs which could be rapidly repurposed if shown to be effective. Any repurposed compounds demonstrating an efficacy signal against usual care will then be considered for further large-scale trials. Compounds that do not demonstrate sufficient efficacy or have safety issues will not be studied further ([name] et al. 2020). The Trial Steering Committee will evaluate the trial data to determine which compounds should be prioritised for further trials, and will review applications/proposals to add new experimental arms to the trial.

A sub-study will also be included as an option for those participants enrolled in Tayside. Neutrophilic inflammation is implicated in increased cardiovascular risk in patients with bronchiectasis and our sub-study will constitute a pilot study to determine if the interventions have an effect on biomarkers of cardiovascular risk.

Rationale for open trial treatments:

Arm 2: Disulfiram

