7.7. Trial assessments

Trial assessments will be performed according to the Schedule of Procedures, Appendix 4. Where trial assessments identify any clinically significant incidental findings, these will be communicated to the participant's GP, with the participant's consent.

Trial assessments will be carried out according to trial specific guidelines.

Missed trial assessments or visits completed outside the visit window will not be reported as breaches where this is due to participant choice or a clinical decision, excursions will be documented, and trial statistician made of aware of discrepancies.

Medical history: focused medical history, taken from medical records and participant reporting, including the following information:

- History of chronic medical conditions related to inclusion and exclusion criteria
- Medication allergies

Review concomitant medications and therapies: taken from medical records and participant reporting at each visit.

Review of AEs: participants will be asked about the occurrence of any AEs since the previous visit, medical records will also be reviewed.

Severity of bronchiectasis: will be evaluated using the Bronchiectasis Severity Index and Medical Research Council dyspnoea score. Exacerbation assessment will use the EMBARC definition of exacerbation (Hill et al. 2017).

Physical examination: a detailed physical examination will be performed at screening to exclude participants with co-morbidities or other clinical disorders that would constitute an exclusion from the trial. This will include the following systems:

- Respiratory
- Cardiovascular
- Abdominal
- Neurological
- Dermatological

Height & weight: as per trial guidelines.

Vital signs: Blood Pressure, pulse, temperature, oxygen saturation as per trial guidelines.

Pregnancy test (urine): will be carried out for women of childbearing potential (WOCBP), as described in section 6.2. See also notes in the exclusion criteria section 6.2, regarding contraception.

Electrocardiogram (ECG): as per trial guidelines, will be reviewed by a doctor prior to randomisation.

6-minute walk test: this test assesses the distance (in metres) an individual can walk in 6 minutes. The participant walks back and forth along a marked walkway of 20 meters at their own pace.

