Spirometry: post bronchodilator spirometry at visits will be carried using American Thoracic Society/European Respiratory Society's guidelines. Forced Expiratory Volume (FEV1) forced vital capacity (FVC) and Forced Expiratory Flow at 25-75% (FEF25-75) will be measured.

Questionnaires: as per schedule of procedures.

Blood samples: collected, processed, and stored as per laboratory manual. Full blood count, urea and electrolytes, liver function tests will be analysed by the local NHS laboratory. Samples will also be taken for trial outcomes. Additional blood samples will be collected for future biomarker and molecular microbiology research, dependent on participant consent, see section 7.2.1. A maximum of 100 ml of blood will be obtained at any visit.

Sputum sample: a sputum sample will be collected, processed, divided and stored as per laboratory manual. Participants will be asked to bring a spontaneous early morning sputum sample with them to visits from their second visit onwards. Where a participant is unable to produce a sputum sample at a visit a hierarchical approach to obtaining sputum samples will be used:

1. spontaneous sputum sample produced at the visit
2. spontaneous early morning sputum brought from home on the day
3. spontaneous early morning sputum brought in within the following 48 hours after the scheduled visit.
4. Induced sputum at sites able to perform induced sputum according to local protocols.

A sputum sample will be analysed locally for active neutrophilic inflammation at screening/baseline using NEATstik.

A sample will also be taken for trial outcomes. Additional sputum sample will be taken for future biomarker and molecular microbiology research, see section 7.2.1.

Nasal sample: brushing of the inferior turbinate will be performed to obtain nasal epithelial cells and the brush then placed into media for storage. Participants should not have a nasal brushing performed if they are receiving anticoagulants (Oral anticoagulants or warfarin) or have a history of deviated nasal septum, base of skull fracture or severe epistaxis. If any of these are present the nasal brushing will be omitted.

Safety assessments: participants will be requested to attend an unscheduled visit if they experience a bronchiectasis exacerbation or any other safety concern.

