9.8. Overdose

An overdose with associated AEs is recorded as the AE diagnosis/symptoms on the relevant AE section in the eCRF. Any dose administered other than prescribed dose for that participant will be reported to the Sponsor as a protocol breach.

If an overdose of trial drug occurs during the trial, then the Investigator or other site personnel will inform the appropriate sponsor representatives immediately, or no later than 24 hours after becoming aware of it. The designated sponsor representative will work with the Investigator to ensure that all relevant information is provided to the sponsor's Pharmacovigilance Committee.

	Treatment	Definition	Treatment
--	------------------	-------------------	------------------

Arm 2	Disulfiram	Exceeding the trial dose of 400mg per day.	Treatment should be symptomatic, and observation is recommended. Supportive therapy should be available, and measures may be necessary to counteract hypotension. Gastric lavage and/or activated charcoal may be considered in cases of disulfiram overdose. Severe vomiting might occur requiring administration of intravenous fluids.
Arm 3	Dipyridamole	Exceeding the trial dose of 400mg per day	Symptomatic therapy is recommended. Administration of xanthine derivatives (e.g. aminophylline) may reverse the haemodynamic effects of dipyridamole overdose. ECG monitoring is advised in such a situation.
Arm 4:	Doxycycline	Exceeding the trial dose of 100mg per day	Discontinue medication. Gastric lavage plus appropriate supportive treatment may be indicated.

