10. STATISTICS AND DATA ANALYSIS

10.1. Sample size calculation

Given the nature of the trial, there is no overall sample size target, but the numbers of participants required for each treatment arm are:

	Treatment	n	Open/closed to recruitment
Arm 1	Usual care	Randomisation will continue to end of trial	Open
Arm 2	Disulfiram	42	Open
Arm 3	Dipyridamole	42	Open
Arm 4	Doxycycline	42	Open

Sample size calculations have been performed using the “Superpower” package in R version 4.2.1 and verified using simulations.

The primary endpoint is sputum NE at day 28. The standard deviation of log₁₀-transformed NE is estimated to be 0.5, using unpublished data from the ORBIT4 trial. A “moderate” standardised difference (Cohen, 1988) of 0.5 between the control and each treatment arm is targeted, which equates to a log₁₀-difference of 0.25, i.e. a reduction in NE of approximately 44% vs control after 28 days of active treatment. The DPP1 inhibitor Brensocatib achieved >90% reduction in NE, so the targeted difference is realistic.

Aiming to recruit the number of participants per treatment arm as above (to allow for up to 10% dropout), with concurrent equal randomisation to the shared control arm, the trial would have >80% power to detect such a difference at the 1-sided 10% significance level. This assumes adjustment for up to 4 covariates in the ANCOVA model, with a modest R² value of approx. 0.1. In reality, the R² value should be larger than this (based on ORBIT-4), so power should be closer to 90% (see Table 10.1.1) (Haworth et al. 2019).

Table 10.1.1. Power, given R² value of covariates, to detect a standardised difference in log₁₀-transformed NE at day 28 of 0.5 between each treatment arm and the shared control at the 1-sided 10% significance level.

R ² value of covariates (with up to 4 covariates)	Power
0.1	81.8%
0.2	85.1%
0.3	88.5%
0.4	91.9%

The design uses the rationale of randomised phase II screening designs in oncology (Rubinstein et al. 2005). By setting the type I error rate to 10% (higher than the conventional 5% for phase III trials but widely accepted in phase II) and targeting a moderate treatment effect size, the required sample size is restricted while maintaining good power. This allows us to quickly and efficiently evaluate multiple treatment options, screening out those that appear suboptimal, and taking forward any showing a sufficiently promising efficacy signal for confirmation in a larger randomised trial.

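### The timing allowances around the day 28 visit run only late while treatment is fixed at 28 days, so the primary NE sample can be taken 2-3 days (at worst 4-5) off drug in the active arms

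*Protocol*

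**What the plan says.** Section 10.1 states that "The primary endpoint is sputum NE at day 28" and targets "a reduction in NE of approximately 44% vs control after 28 days of active treatment". The effect the trial is sized for is therefore an effect on treatment.

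Section 2 says "Treatment will be administered for 28 days". The table in Section 8.7 gives 28 days for each open arm, and Appendix 4 marks dispensing once, at Visit 2.

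On timing, Appendix 4 allows only lateness: "If a participant is unable to attend on the day of visit a delay of up to 2 days is accepted". It gives no early allowance. Section 7.7 adds an allowance for the sample itself: "Where a participant is unable to produce a sputum sample at a visit a hierarchical approach to obtaining sputum samples will be used". The third step of that hierarchy is "spontaneous early morning sputum brought in within the following 48 hours after the scheduled visit". Section 7.7 also says that "visits completed outside the visit window will not be reported as breaches where this is due to participant choice or a clinical decision".

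No section ties the primary sputum sample to the last dose or limits the gap between them.

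**The concern.** Both stated timing allowances push the primary sample later, and the course of drug does not stretch with them. Full compliance with the schedule can therefore produce an off-treatment value at the single primary timepoint. This differs from a participant who stops early, which an intention-to-treat analysis is meant to absorb. Here the schedule itself creates the gap.

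The effect is one-sided. A late sample in usual care reflects the same care as a timely one. A late sample in an active arm reflects some days without drug, and if the effect wanes the contrast shrinks toward zero. Section 2 says that compounds without sufficient efficacy will not be studied further, so the cost is a higher chance of discarding an active compound. ANCOVA and multiple imputation (Section 10.3) do not correct a value that was observed, but observed off drug.

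**Working it through.** **1. Calendar.** Inputs: 28 days of treatment (Section 8.7), visit on day 28 with up to 2 days' delay (Appendix 4), sputum up to 48 hours later (Section 7.7). The day of first dose is not stated, and baseline is day 1 in Section 7.6 but day 0 in Appendix 4. A first dose on day 0 puts the last dosing day on day 27; a first dose on day 1 puts it on day 28.

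Days off drug = visit day + sputum delay − last dosing day.

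| Visit | Sputum | Last dose day 28 | Last dose day 27 |
|---|---|---|---|
| Day 28 | at visit, day 28 | 0 | 1 |
| Day 28 | 48 h later, day 30 | 2 | 3 |
| Day 30 | at visit, day 30 | 2 | 3 |
| Day 30 | 48 h later, day 32 | 4 | 5 |

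The last row needs the 48 hours to run from the attended visit. If they run from the planned date, the latest sample is day 30, and the gap is 2-3 days.

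**2. The plan's own power.** Inputs from Section 10.1: standardised difference 0.5 (0.25 on the log10 scale, SD 0.5), one-sided 10% level, 42 per arm with up to 10% dropout, up to 4 covariates. 42 × 0.9 = 37.8, taken as 37 evaluable per arm.

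- d = 0.5/√(1 − R²); degrees of freedom = 2 × 37 − 6 = 68
- variance inflation for four covariates = 1 + 4/(2 × 37 − 7) = 1.060
- power from the noncentral t with noncentrality d × √(37/(2 × 1.060))

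For R² = 0.1, 0.2, 0.3 and 0.4 this gives 81.8%, 85.1%, 88.5% and 91.9%, which matches Table 10.1.1 exactly. The stated power figures are not in error. The target also checks: 1 − 10^(−0.25) = 43.8%, the stated 44%.

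**3. Dilution (assumptions).** The protocol gives no rate at which the effect wanes and no share of late samples. I assume exponential waning with half-life h of 3, 7 or 14 days, and a share q of active-arm samples taken t days off drug. The SD is left unchanged.

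- retained effect r = 0.5^(t/h)
- arm-level standardised difference = 0.5 × [1 − q(1 − r)]

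For q = 10% and t = 3 days, at R² = 0.1:

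| h (days) | r | Standardised difference | Arm-level NE reduction | Power |
|---|---|---|---|---|
| 3 | 0.500 | 0.475 | 42.1% | 78.7% |
| 7 | 0.743 | 0.487 | 42.9% | 80.3% |
| 14 | 0.862 | 0.493 | 43.3% | 81.0% |

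Sensitivity, for half-lives of 3 / 7 / 14 days:

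- q = 10%, t = 5 days, R² = 0.1: 77.6% / 79.4% / 80.5%
- q = 20%, t = 3 days, R² = 0.1: 75.4% / 78.7% / 80.1%
- q = 10%, t = 3 days, R² = 0.3: 85.9% / 87.2% / 87.8%, against 88.5%

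As a bound, if 10% of samples had lost the whole effect, power at R² = 0.1 would be 75.4%.

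**4. Cost of dropping late samples instead.** Losing 10% in each arm leaves 37 × 0.9 = 33.3 per arm. At R² = 0.1, with nothing recovered by imputation, power is 78.4%. That is below the 80.3% from keeping the samples at 3 days off drug with a 7-day half-life.

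**The case against.** The strongest reply is that the long gap is a corner case. Day 32 requires a visit 2 days late, no sample brought from home, none produced at the visit, and a sample a full 48 hours later. Section 6.1 enrols people who normally produce sputum daily, and Section 7.7 already asks them to bring an early-morning sample. The 48-hour option is only the third step. All of this stands: 4-5 days is a permitted extreme, and 2-3 days is the figure to plan around.

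A reader might go further and infer that every permitted deviation moves the sample off treatment. The text does not say so. The other steps of the hierarchy add no stated delay, and the tolerance for visits outside the window, which covers participant choice and clinical decisions, is not limited to late ones. That same tolerance means day 32 is not a hard ceiling.

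A reader might also take Section 9.8, "Any dose administered other than prescribed dose for that participant will be reported to the Sponsor as a protocol breach", as proof that dosing cannot be extended to meet a late visit. That sentence sits under overdose and concerns the dose given, not the length of the course. The fixed duration rests on Sections 2 and 8.7.

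Finally, Section 7.7 requires excursions to be documented and the statistician told. Section 10.3 leaves sensitivity analyses to the statistical analysis plan, and sample handling is left to the Laboratory Manual. Neither document is shown, so missing sample times or a missing sensitivity analysis cannot be claimed. Those documents could describe or explore late samples, but they would not change a window that the protocol sets only on the late side.

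**Conclusion.** The point holds as a design weakness of modest expected size. The protocol's own rules let the primary NE sample fall 2-3 days after the last dose when one allowance is used. They permit 4-5 days if both are stacked and the 48 hours run from the attended visit. Any resulting bias is toward no effect and arises only in the active arms.

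Its size cannot be fixed from the document. With 10% of active-arm samples 3 days off drug and half-lives of 3 to 14 days, power at R² = 0.1 falls from 81.8% to about 79-81%. The loss is larger with more late samples or faster waning. Section 10.1 expects a larger R², where there is more margin. At R² = 0.1 the claim of more than 80% power has under 2 points to spare.

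Two stronger conclusions are not supported. The documents do not show that the endpoint is routinely measured 4-5 days off drug. Nor do they support removing late samples from the primary analysis: that can cost more power than it saves, and it sits badly with intention-to-treat because lateness may be related to illness.

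**What to change.** - For Visit 5 in all arms, put the window on the early side (e.g. day 26 to day 28) in Appendix 4. The primary sputum is then normally collected while treatment is ongoing, with the early-morning home sample as the default.
- State in Section 7.7 whether the 48 hours run from the planned date or the attended visit.
- Reconcile the treatment-duration, visit-window and sputum-collection text, including whether baseline is day 0 or day 1. No change to dosing is involved.
- Record the date of the sputum sample and the date of the last dose.
- Keep late samples in the intention-to-treat primary analysis. Add a sensitivity analysis limited to on-treatment samples, with the cut-off fixed in advance (for example, no later than the day after the last scheduled dose).

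The cost is wording in Appendix 4 and Sections 7.6 and 7.7, two eCRF fields if they are not already there, and one sensitivity analysis. The downside is that some participants will be sampled after 26-27 rather than 28 days of drug. Applying the window to usual care as well keeps the arms comparable in timing.
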